**A. Study Population and Eligibility**

This is a prospective randomized pilot study including between 36-39 subjects with cardiomyopathy (CM) and high PVC burden with a likely diagnosis of PVC-CM, where all subjects will be assigned to a 1:1 random allocation to one of two un-blinded PVC suppression groups: 1) PVC radiofrequency ablation (RFA) vs. 2) antiarrhythmic drugs (AADs).

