A 2-week ambulatory ECG Holter (Zio Patch, IRhythm, Inc.) will be obtained 4-6 weeks after initiation of AAD to assess whether PVC suppression was successful (defined above). If successful PVC suppression is not achieved, we will ask sites to consider either an increase in the antiarrhythmic dose or change of antiarrhythmic as noted above. A repeat 2-week ambulatory Holter monitor will be done 4 weeks after adjustment of AAD to re-assess PVC suppression.

Radiofrequency Ablation (RFA) of PVCs. RFA will be performed after completion of 3-month observation period). EPS will be performed on their baseline medications, except for antiarrhythmic drugs class II (beta blockers) which will be held at least 5 half-lives prior to procedure. Beta blockers should be resumed after RFA.

EPS and RFA will be performed using standard techniques and protocols similar to those subjects that do not participate in this clinical study. Multipolar electrode diagnostic catheters will be inserted. If no ectopy is present at baseline, isoproterenol may be infused at rates up to 10mcg/min. If the ectopy is infrequent despite adrenergic stimulation, pace mapping will be performed at a pacing cycle length determined by coupling interval of the spontaneous ventricular ectopy. RV or LV PVCs will be mapped/ablated at the discretion of the electrophysiologist. Coronary angiography and/or intracardiac echo will be performed as needed. RFA will be performed at the site of earliest endocardial activation or best pace map. RFA applications will be delivered for at least 30 seconds if adequate power at the electrode-tissue interface is achieved. RFA will be continued for at least 60-120 seconds in sites where PVCs are abolished within 30 seconds. After ablation of the PVCs, isoproterenol will be administered at 2-10 mcg/min as required to shorten sinus CL to 500ms to confirm that PVCs are not inducible by adrenergic stimulation. In the event of polymorphic PVCs, all morphologies are to be targeted for ablation. Subjects will be observed overnight in a telemetry bed and discharged home the next day, as it is current standard of care.

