**Table 3. End-points for PAPS Pilot study**

Primary End-points
- Improvement of LVEF
- Responders to PVC suppression strategy (delta LVEF $\geq$ 10%)
Secondary End-points
- Successful PVC suppression ( $\downarrow$ PVC burden $\geq$ 80%)
- Composite end-point of adverse events 
 
- Worsening NYHA functional class (I-IV)
 
- Number of HF and cardiac-related Hospital admissions
 
- RFA complications / AAD adverse effects
 
- Cardiovascular death
 

- Composite end-point of arrhythmia burden: 
 
- PVC recurrence (PVC reduction < 80 % after RFA or AAD)
 
- Non-sustained and sustained ventricular arrhythmias
 
- Arrhythmic sudden cardiac death.
 

Subjects that refuse enrollment, will be asked to participate in a PVC-CM registry to follow their response and crossover to different treatment strategies (described above Section A.1)..

We hypothesize that subjects and/or physicians will not object to participate due to the 3-month observation period since most tertiary referral centers have significant procedure wait times for which usually they are scheduled between 8- to 12-weeks after clinical decision of PVC suppression is made. We have involved all participating centers, who agree that this is a common and acceptable scenario during which the observation period proposed could take place. In contrast to other clinical studies where RFA is being compared to placebo, we speculate that randomization of RFA vs. AADs will not be an enrollment limitation since all subjects will undergo a PVC suppression strategy. *This pilot study will allow us to prove feasibility of the PAPS study with the current study design including a 3-month observation period and treatment randomization.*

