a. Adverse event (AE) grading and attribution scale. The investigator will try to determine the relationship of adverse event to RFA and/or AAD therapy as not related, possibly related, or definitely related using standard criteria for clinical trials. All grades of toxicity will be noted.

The following grading and attribution scale will be employed:

- 0 = No adverse event or within normal limits
- 1 = Mild AE, not requiring treatment
- 2 = Moderate AE, resolved with treatment
- 3 = Severe adverse event (SAE) is any untoward medical occurrence that at any point during the study:
  - Results in death
  - Life-threatening – refers to an event in which the subject was at risk of death at the time of the event; it does not refer to an event which hypothetically might have caused death if it were more severe.
  - Requires in-patient hospitalization or prolongation of existing hospitalization – Hospital admission is usually interpreted as requirement of at least one overnight stay in subjects in the medical therapy arm or PVC suppression; whereas in subjects in the PVC suppression arm, a prolonged hospital stay will be defined if more than two days of hospital stay is required after RFA ablation. Treatment and release from an emergency department generally does not qualify as a hospitalization, unless the event qualified as an SAE based on other criteria.
  - Results in persistent or significant disability/incapacity
  - Considered medically significant by the investigator or requires intervention to prevent any of the outcomes above. Medically significant are those events considered important in the investigator's opinion and which may not be immediately life-threatening or result in death or hospitalization but may jeopardize the subject or may require intervention to prevent one of the outcomes listed in the definition above.

b. Reporting of Adverse Events (AE)

The Investigator and/or research coordinator at each participating center will be responsible for collecting data in regard to adverse events. The investigator must decide whether each incident meets the definition of a SAE.

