A Data and Safety Monitoring Board (DSMB) will consist of 2 heart failure specialists (Drs. [name] and [name]) and a cardiac electrophysiologist ([name]) (see letters of support) that have no direct investment in the study to prevent jeopardizing subject safety. In addition to the IRB, the DSMB will review the research protocol and plans for data safety and monitoring, evaluate the progress of the trial with periodic assessments of data quality and timeliness, participant recruitment, accrual and retention, participant risk versus benefit, and reports from related studies.

The DSMB will meet every 4 months to review data and adverse event reports. Additionally, they will meet to review interim analysis when available. This will be performed in a closed session with open access to the PI if requested by the Board. Data monitoring will focus on several areas: 1) Performance, which will allow us to assess site performance with respect to subject recruitment, retention and follow-up, flow of data forms, protocol adherence and quality of data; 2) Safety, which allows us to assess the magnitude of adverse events; and 3) Treatment, in order to monitor and assess treatment effects.

The DSMB has the responsibility to make written reports of their findings and recommendations to the Coordinating Center, IRB, NIH/NHLBI (funding institution) and investigators concerning continuation or conclusion of the trial if it considers that RFA has a significantly higher benefit or increased risk as compared to the control arm. Annual data safety, adverse event reports and interim analyses may result in the need to revise the informed consent, or other study documents, for which the PI must submit a study amendment to the IRB. This could result in early study termination only if continuation will not produce benefit to subjects or if the treatment outcome is known to have benefit.

In accordance with the terms of the Federal Wide Assurance, the Office for Human Research Protections (OHRP) and the Federal Drug Administration (FDA) will be notified in a timely manner of 1) serious or continuing noncompliance; 2) significant adverse events involving risk to participants or others; or 3) suspension or termination of IRB approval for a study.

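### The SAE hospitalization rule names arms this trial does not have, and its undefined two-day limit after RFA may leave out one complication-driven extra night that would count on AAD

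*Combined protocol and SAP*

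**What the plan says.** Part I, section A (Study Population and Eligibility) randomizes subjects 1:1 to "one of two un-blinded PVC suppression groups", RFA or AAD. The discussion around Table 3 expects randomization not to limit enrollment, "since all subjects will undergo a PVC suppression strategy". The opening of the Data Safety Monitoring Plan also describes the comparison as RFA against AAD.

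Item a of that plan (adverse event grading and attribution scale) lists inpatient admission, or lengthening of a stay already under way, as one route to an SAE. It then interprets the two halves separately:

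- Admission is usually taken to mean "at least one overnight stay in subjects in the medical therapy arm or PVC suppression".
- For prolongation, "in the PVC suppression arm, a prolonged hospital stay will be defined if more than two days of hospital stay is required"; the sentence goes on to limit this to the stay following ablation.

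The unit of days is not defined, and no prolongation limit is given for AAD. Part I, section D describes the planned stay after RFA: "Subjects will be observed overnight in a telemetry bed and discharged home the next day".

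Item d of the same plan has the DSMB report on whether to continue or conclude the trial if it considers that RFA has a "significantly higher benefit or increased risk as compared to the control arm".

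**The concern.** Item a is the text from which an investigator decides whether an event is serious. It is written for a trial that compares medical therapy with PVC suppression, which is not this trial. No subject is in a medical therapy arm, and the PVC suppression label fits everyone. The control-arm label in item d is a third name that matches neither randomized arm, and the Potential Risks section uses the word control for the three-month observation period.

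The special limit for the post-RFA stay also does not visibly correspond to the stay that section D plans. If it is looser than that stay, a complication that keeps a subject in hospital one night longer than planned could be left unclassified as an SAE after RFA, while the same prolongation on AAD would be classified as one. Because the unit is undefined, sites could also classify identical events differently. At stake are the SAE label, the 24-hour notification that goes with it, and the consistency of the SAE tables from which the DSMB compares RFA with AAD.

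**Working it through.** No figure in the plan needs to be reproduced. The check applies the wording of item a to the stay planned in section D.

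**Inputs.** Arms: RFA and AAD (Part I, section A). Admission threshold: one overnight stay, with both labels named (item a). Prolongation threshold after ablation: more than two days (item a). Planned post-RFA stay: one night, home the next day (section D), which is 1 night but touches 2 calendar days. In every row the event is assumed to be untoward, since item a requires that; the planned night alone is therefore not an SAE. Only the hospitalization criterion is tested.

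| Event | AAD subject | RFA subject |
|---|---|---|
| New unplanned admission, one night | Meets criterion | Meets criterion, because the admission rule also names PVC suppression |
| One extra night, days counted as nights or completed 24-hour periods | Meets criterion: no limit stated, so the general prolongation wording applies | Post-ablation stay: 1 + 1 = 2; 2 is not more than 2, so not met |
| One extra night, calendar days | Meets criterion | Post-ablation stay: 2 + 1 = 3; 3 is more than 2, so met |
| Two extra nights, either count | Meets criterion | Post-ablation stay: 1 + 2 = 3 nights, or 2 + 2 = 4 calendar days; both are more than 2, so met |

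The arms differ in one row only: a single extra night on the post-RFA stay, with days read as nights or completed 24-hour periods.

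**Can it be sized?** Enrollment is 36 to 39 subjects at 1:1. That is 18 per arm at 36 (36 / 2), and the sample size section gives up to 20. The stated RFA risk is 1-2% (section J, Risk Benefit assessment) or 2-3% (Data Safety Monitoring Plan, item c). With one procedure per subject, expected complications run from 18 x 0.01 = 0.18 to 20 x 0.03 = 0.60. The events at issue are the part of these that add exactly one night and meet no other SAE criterion. The documents do not give that fraction, so the effect cannot be computed.

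**The case against.** The strongest reply is that this is a matter of leftover labels. The one-night rule names both labels and so reaches every subject. The two-day rule is limited to the stay after ablation, so the labels alone rarely change a classification. In a two-arm trial, a control arm set against RFA most naturally means AAD. Some allowance for a procedure with a planned night is legitimate. With calendar days, the limit already means any stay longer than planned. All of this stands, and it narrows the point to the undefined unit, its fit with section D and the labels.

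Four stronger readings are tempting, and the documents do not support them:

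- *Each arm has its own length-of-stay threshold.* It does not. An RFA subject readmitted for one night meets the criterion exactly as an AAD subject does.
- *The rule favors RFA on the adverse-event hypothesis.* That hypothesis concerns a composite. Section E gives the composite its own admission definition, common to both arms and including emergency department visits, and counts RFA complications without any seriousness threshold.
- *Short-stay RFA complications are hidden from the DSMB.* Section C, item c.6 sends all adverse events to the Coordinating Center within 24-48 hours and has procedure complications adjudicated. The DSMB reviews all adverse events every 4 months with full access to records.
- *One reclassified event moves the RFA arm's SAE rate by 5.0 to 5.6 percentage points, so the effect is large.* This is only 1/20 to 1/18. It holds for any event in an arm of that size and says nothing about how often this one occurs.

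An event that misses the stay criterion can also qualify as medically significant, or as needing intervention to avert a listed outcome. That safeguard is real, but the medically significant limb rests on the judgment of an unblinded investigator. It does not replace a clear rule.

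**Conclusion.** The point holds in a limited form. The mislabeling needs no interpretation: item a and item d use arm names that do not match the randomized arms. The difference between arms is conditional. It exists if days mean nights or completed 24-hour periods, is confined to one complication-driven extra night on the post-RFA stay, and disappears if calendar days are meant.

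Where it exists, it affects whether the event is called an SAE, whether the expedited route applies, and what the SAE tables show the DSMB. It does not reach the secondary composite, and it does not remove events from the DSMB's view. The documents plan no hospital stay for starting an AAD, so the comparison on that side arises only when a subject is already in hospital for another reason.

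The size cannot be quantified from the documents and is probably small in a pilot of 36 to 39 subjects. The correction is still worth making, because the sentence decides seriousness at 12 or more centers and can at present be read in two ways.

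**What to change.** In item a of the Data Safety Monitoring Plan:

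1. Name the arms RFA and AAD.
2. State how length of stay is counted (nights, 24-hour periods or calendar days).
3. Reconcile the prolongation threshold with the post-procedure stay described in section D.
4. Apply one reporting rule to both arms: a stay planned by the protocol is not itself an SAE, and a stay lengthened beyond it by an untoward event counts as prolongation in either arm. Tying the rule to the planned stay also covers an AAD subject who crosses to ablation after 6 months and stays in the intention-to-treat analysis.

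In item d, replace the control-arm label with AAD arm.

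The cost is a wording change in the Data Safety Monitoring Plan, a matching instruction on the case report form, and slightly more SAE reports from the RFA arm. Treatment, visits and sample size do not change.

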### **Risk Benefit assessment**

All PVC suppression strategies (RFA and AADs), proposed in this grant application are approved by the Heart Rhythm Society and FDA for the treatment of ventricular arrhythmias, respectively. Subjects assigned to the RFA arm may have a small risk of minor or major complications related to RFA of PVCs. However, these risks associated with RFA of PVCs are acceptable and RFA of PVCs continues to be performed in clinical practice even though there is limited data to support benefit from this intervention. Risks associated with RFA are small (1-2%) including but not limited to stroke, myocardial infarction, coronary artery injury, bleeding, cardiac tamponade, pneumothorax, atrioventricular block with subsequent need for permanent pacemaker, and even death. Similarly, antiarrhythmic drugs (AAD) may have long-term risks/adverse effects based on the antiarrhythmic chosen (e.g. amiodarone has significant long-term effects including lung disease such as decrease in lung diffusion capacity, optical neuritis, abnormal thyroid and liver function, and pro-arrhythmic effects; see Section C in Protection of Human Subjects document for details). Yet, these treatment options are currently standard of care frequently offered to this subject population with known complications and these adverse events. To minimize the potential risks with AADs, all subjects should be considered for additional safety laboratory analyses during treatment as recommended per guidelines based on AAD chosen (amiodarone - TSH, LFTs, PFTs, eye exam).

A pregnancy test will be obtained on females of childbearing age that are assigned to the RFA treatment prior to procedure due to fluoroscopy exposure. In contrast, a pregnancy test will be performed on a monthly basis on those randomized to the antiarrhythmic treatment arm to confirm the lack of pregnancy throughout the 12-month follow up period. If a female on antiarrhythmic arm becomes pregnant during the 12-month follow up period, we will consider stopping antiarrhythmics and the subject will be withdrawn from the study.

The IRB should be notified of any serious adverse events (SAE) within 24 hours of such event or knowledge of the event. Additionally, the PAPS National Research Coordinator should be notified within 24 hours of the event or knowledge of the event. The investigator must decide whether each incident meets the definition of a SAE.

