## DATA SAFETY MONITORING PLAN

---

The PAPS Pilot study is a national multicenter randomized control study to enroll between 36-39 subjects with cardiomyopathy associated with frequent PVCs. This is a phase IV trial with moderate risk as participating subjects will be randomized to two different strategies (RFA versus AAD) commonly used in clinical practice to treat subjects with frequent PVCs. We consider this study to be moderate risk since most subjects with a suspected PVC-CM would undergo RFA as a common clinical practice (as discussed above). All research performed under this study will conform to laws, regulations and VA policies and procedures pertaining to protections for human subjects.

In addition to Coordinating Center and central IRB oversight, a Data Safety Monitoring Board (DSMB) will be organized according to the FDA recommendations to review all serious adverse events as well as study progress (including all adverse events) every 4 months after study initiation. The DSMB will be integrated by faculty members from institutions without active enrollment in the study and without a vested interest in the proposed research that have different expertise (see DSMB section in Protection of Human Subjects document). The members of the DSMB will have full access to all study records and will have the authority to discontinue the study at any time. Please consult the Protocol in Appendix for additional details.

A detailed Data and Safety Monitoring Plan (DSMP) will be submitted to the IRB and NIH (funding institution) for approval prior to the accrual of human subjects. The Data Safety Monitoring Plan is written to ensure the safety of the participants and verifying the validity and integrity of the data.

During each scheduled visit and in between visits, subjects will be asked and instructed to call in regard to any event out of the ordinary. Those subjects randomized to the RFA group will be evaluated immediately, throughout the first 24 hours and 1-2 weeks after the procedure by the research team as standard follow up on any of these procedures. It will be the responsibility of the investigator/coordinator to assess the subject personally and request laboratory or any appropriate tests if needed. All adverse events including serious adverse events (SAE) will be monitored for all subjects during their participation in this study.

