*Reporting Requirement:* Once the local Principal Investigator (PI) determines that an adverse event meets the IRBs' reporting requirements, he/she must report the SAE and related safety information to the Coordinating Center on the required *Significant Adverse Event Report Form* (See form attached) provided for this purpose. Supporting documents, including a copy of the Informed Consent, should also be emailed/submitted through REDCap. For reasons of confidentiality, subject's names must not be included in the report. Additionally, local SAEs must be reported to the IRB of record per policy. If the adverse event results in the need to revise the informed consent, or other study documents, the PI will submit a request for a modification through the Coordinating Center to the IRB of record.

c. Annual Data and Adverse Events Report

This report will be prepared annually by the PI and research coordinator at the Coordinating Center. This report will include the number of subjects actively enrolled, those that abandon and complete the research protocol, as well as, all side effects and adverse events in both groups.

In addition, an interim analysis or treatment monitoring will be performed by VCU Research Incubator. Due to a small risk related to RFA (estimated 2-3%), this interim analysis will be performed once the first 15 subjects (half of sample size) have completed a 15-month protocol. Data reports and interim analysis will be reviewed by the IRB at the Coordinating Center and DSMB during its convened meetings.

d. Data management and safety review

Collaborating centers and the Coordinating Center shall immediately notify each other, and the Coordinating Center shall promptly notify the IRB, upon identifying any aspect of the Protocol, including unanticipated problems involving risk and information discovered during site monitoring visits/remote monitoring visits or in the study results that may adversely affect the safety, well-being, or medical care of subjects, or that may affect the willingness of subjects to continue participation in the research, may influence the conduct of the study, or may alter the IRB's approval to continue the study. When subject safety could be directly affected by study results, the Coordinating Center will notify participating sites who will provide written communication to affected subjects.

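### The early-termination wording leaves out increased risk, which the same section names as a ground for conclusion, and the interim linked to RFA risk comes after essentially all first ablations on the planned accrual

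*Combined protocol and SAP*

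**What the plan says.** **Grounds for ending the study.** The opening of the DSMP says that DSMB members "will have the authority to discontinue the study at any time". Item d (Data management and safety review) has the DSMB report on continuation or conclusion if it considers that "RFA has a significantly higher benefit or increased risk as compared to the control arm". The next sentence says that annual safety data, adverse event reports and interim analyses may lead to revised study documents. The one after it limits what else may follow from them: "early study termination only if continuation will not produce benefit to subjects or if the treatment outcome is known to have benefit".

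**The interim.** Item c (Annual Data and Adverse Events Report) announces an interim analysis or treatment monitoring. The reason given begins "Due to a small risk related to RFA (estimated 2-3" (the figure is a percentage), and the sentence continues: "this interim analysis will be performed once the first 15 subjects (half of sample size) have completed a 15-month protocol". The Risk Benefit assessment in section J gives a different figure: "Risks associated with RFA are small (1-2" (again a percentage).

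**Routine monitoring.** The DSMB is to "review all serious adverse events as well as study progress (including all adverse events) every 4 months after study initiation". The annual report covers "all side effects and adverse events in both groups". RFA subjects are evaluated immediately, over the first 24 hours, and 1 to 2 weeks after the procedure (DSMP opening).

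**The concern.** The two statements of grounds in item d do not agree. Increased risk is a reason to recommend conclusion, but the later sentence introduces an exclusive list with *only if*, and risk is not on it. That sentence governs what the safety reports and interim analyses may lead to, which is where a harm signal would appear. A DSMB that followed it to the letter could not end the study on harm. One that followed the DSMP opening could. The comparator is also undefined: both randomised arms are active, so no arm is plainly a control arm.

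The second matter is timing. An interim prompted by the risk of a procedure is most useful while procedures are still to be done. A trigger counted in 15-month completers comes almost a year after each of those subjects' own ablation, and the plan does not say whether first procedures will remain by then.

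Third, item d allows conclusion for benefit, and the interim could feed that decision with about 7 to 8 subjects per arm in a pilot whose purpose is feasibility and planning data for the full PAPS trial.

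**Working it through.** **1. Grounds for ending the study, side by side**

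| Place | Increased risk | Benefit | No benefit |
|---|---|---|---|
| DSMP opening | any reason, at any time | any reason | any reason |
| Item d, DSMB recommendation | yes | yes | not named |
| Item d, early termination (*only if*) | **not listed** | yes | yes |

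The third row cannot be applied literally together with either of the first two. No assumption is needed.

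**2. The plan's own figure.** 15 = 30/2, where 30 is the pilot base in Sample size justification (section I). Against the 36 to 39 to be enrolled, 15/36 = 41.7% and 15/39 = 38.5%; half would be 18 to 19.5.

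**3. When the interim falls.** Inputs: N = 36 or 39; recruitment complete at month 18 (K. Timeline); first RFA on day 84 to 105 and last visit at Week 64, day 441 to 454 (Table 2). Assumptions: even accrual, no losses, 30.44 days per month, enrolment starting at month 0 or month 2 (Table 4 marks half of the first four-month block).

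Trigger = start + (15/N) × (end − start) + 448/30.44, where 448 days is Week 64 and equals 14.72 months.

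| End of accrual | Start | N | 15th enrolled (month) | Trigger (month) |
|---|---|---|---|---|
| 18 | 0 | 36 | 7.50 | 22.2 |
| 18 | 0 | 39 | 6.92 | 21.6 |
| 18 | 2 | 36 | 8.67 | 23.4 |
| 18 | 2 | 39 | 8.15 | 22.9 |
| 24 | 0 | 36 | 10.00 | 24.7 |
| 24 | 0 | 39 | 9.23 | 24.0 |
| 24 | 2 | 36 | 11.17 | 25.9 |
| 24 | 2 | 39 | 10.46 | 25.2 |

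The earliest visit day (441) moves the earliest 18-month value to 6.92 + 14.49 = 21.4. The latest (454) adds 0.2 month. Losses push the trigger later.

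Last first RFA = end + 84/30.44 to end + 105/30.44:
- 18-month accrual: 18 + 2.76 to 18 + 3.45 = month 20.8 to 21.5.
- 24-month accrual: month 26.8 to 27.5.

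First RFAs left = (last first RFA − trigger) × N/(end − start) × 1/2:
- 18 months: zero with the last visit at Week 64. The most extreme combination (N = 39, last visit on day 441, RFA on day 105) leaves 0.04.
- 24 months: from (26.76 − 25.88) × 36/22 × 1/2 = 0.7 to (27.45 − 23.95) × 39/24 × 1/2 = 2.8, so about 1 to 3.

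The 24-month case matters because Enrollment, Retention and Follow up Plans reckons on at least 3 treated subjects per centre in 2 years. In simulations with flat, front-loaded and back-loaded accrual, with and without losses, the mean number left was 0 to 0.4 at 18 months and 0 to 2.6 at 24 months.

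DSMB meetings before the trigger on the 18-month calendar: months 4, 8, 12, 16 and 20, so five.

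**4. What 15 completers can say about benefit.** From the sample size inputs (baseline SD 5, 12-month SD 10, correlation 0.25), the SD of change is √(25 + 100 − 2 × 0.25 × 5 × 10) = 10. With 7 and 8 subjects, the 95% half-width is t(13) × SD × √(1/7 + 1/8) = 2.160 × 10 × 0.5175 = 11.2 points. With an SD of 9.7, allowing for baseline adjustment, it is 10.8. The assumed difference is 40 − 35 = 5.

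**5. An earlier, procedure-based look.** Trigger: 9 to 10 RFA subjects treated and 14 days past the procedure, losses 0 to 15%.
- Earliest on 18-month accrual: (9/18) × 18 + (84 + 14)/30.44 = month 12.2.
- Latest: 2 + (10/19.5)/0.85 × 16 + (105 + 14)/30.44 = month 15.6.
- On 24-month accrual: month 15.2 to 19.2.
- About 6 to 9 first RFAs are still to come in each case.

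Precision is low. The chance of at least one event, 1 − (1 − p)^n, is 17% (n = 9, p = 2%) to 26% (n = 10, p = 3%). With no events, the one-sided 95% upper limit, 1 − 0.05^(1/n), is 28% to 26%. The 7 to 8 RFA subjects among 15 completers do no better: 13% to 22%, upper limit 35% to 31%. The gain is in timing only.

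**The case against.** **Harm is already monitored.** A reader might infer from the *only if* sentence and the late interim that RFA harm goes unwatched. The documents do not support that. All adverse events reach the DSMB every 4 months, the DSMB can stop the study at any time, and item d itself names increased risk. This stands. It limits the point to conflicting wording and to an interim that adds little on first-procedure risk. It also means that an earlier safety summary would partly duplicate the routine review.

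**The late trigger may be deliberate.** The risk clause can be read as saying that the risk is low enough for one late look. Nor is it right that the interim has no stated purpose: item c calls it treatment monitoring, item d lists treatment effects among the areas monitored, and completers suit the 12-month adverse event composite in section E. It could also still inform redo ablations, later crossovers and consent wording. This stands, and is why keeping the trigger with a stated purpose is an acceptable remedy.

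**Harm might be covered by the no-benefit ground.** Perhaps, but a reader should not have to stretch an exclusive list to reach a ground named two sentences before.

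**15 may not be a mistake.** The 6 to 9 extra subjects allow for spontaneous improvement during observation, and subjects who no longer qualify at Week 12 are withdrawn. For a count of completers, 30 is a defensible base. It needs a clarifying phrase, not a new number.

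**The Data Sharing Plan is not a stopping rule.** Its statement that the pilot is not meant to answer the benefit question concerns how shared data are interpreted. It sits uneasily with concluding for benefit but is not a rival rule. Nor do the documents say that early conclusion would end follow-up of treated subjects, so lost data cannot be claimed as a certain consequence.

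**Conclusion.** The conflict over grounds is wrong as written and rests on the text alone: item d names increased risk and then omits it from an exclusive list, against an unrestricted authority in the DSMP opening.

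The timing point is an inexpensive improvement. It rests on roughly even accrual, which the plan does not state. At 18 months essentially no first RFAs remain at the interim; at 24 months about 1 to 3 do. Confidence here is moderate, because the sentence giving the reason can be read two ways.

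The benefit point is a precaution. The plan specifies no LVEF comparison or boundary for this interim, so the half-width of about 11 points shows what such a comparison could deliver, not what a planned test will deliver. The documents also do not settle whether the control arm means the AAD arm, since they use *control* for the observation period that every subject passes through. That is for the sponsor to say.

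**What to change.** All changes are to DSMP wording, with one figure to align in section J.

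1. Reconcile the sentences in item d with each other and with the DSMP opening, so that increased risk is a ground throughout. Say which arm the control arm means.
2. Choose one for the interim:
   - present an RFA-safety summary, with adverse events in both arms, at an existing 4-monthly DSMB meeting once about half of the planned RFA subjects (9 to 10) have had the procedure and the 1 to 2 week evaluation; or
   - keep the 15-completer trigger and state that it is for treatment monitoring and 12-month adverse events, not for first-procedure risk.
3. State that the pilot will not be concluded early for superior LVEF or responder benefit.
4. Clarify that 15 is half of the base of 30, not of the 36 to 39 enrolled, and reconcile the 1-2% and 2-3% RFA risk figures.

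Cost: no extra meeting and no new data. The first option in item 2 overlaps with routine review, has little AAD follow-up at that date and gives little precision. Item 3 gives up an early efficacy conclusion that the data could hardly support.
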